9.2 SAMPLE SIZE DETERMINATION

The sample size is 48 participants in the final dataset to be used in analysis. However, to ensure that 48 participants complete the experiment, we conservatively estimate to enroll 100 participants as a ceiling for the sake of IRB approval. The motivation for the sample size of 48 participants in the analysis is explained below. The sample size is determined based on previous experiments from our group: the effect size of previous findings and the reliability of our estimates. Our estimators are precise due to sufficient number of trials per condition with each participant and that the tasks are titrated to the individual.

Primary outcome: Cross-frequency transcranial alternating current stimulation (tACS) to lateral frontal cortex at delta-beta frequency will increase goal-directed behavior relative to placebo stimulation.

Previous Data: The planning and refinement of the proposed study was informed by our previous experiments that serve as preliminary data for the proposal. In our previous experiment, we delivered cross-frequency tACS to lateral frontal cortex at delta-beta frequency to modulate performance on a cognitive control task relative to placebo stimulation (Riddle, McFerren et al. 2021). As in the current proposal, a specific component of the task was identified to drive an increase in delta-beta coupling. This was the component that was altered by delta-beta tACS. In the previous experiment, we found a significant interaction between stimulation (delta-beta tACS or theta-gamma tACS, minus placebo) and our cognitive control dimension of interest with a partial-eta square of 0.288 with $N = 23$. For the specific comparison of interest, we found increased reaction time relative to placebo with an effect size of 0.480 from pair-wise t-test with $N = 23$.

Sample Size Determination and Power Calculation: Our previous effect size based on behavioral modulation from delta-beta tACS used a crossover design. The experiment proposed here will use a parallel arm design; however, we will calculate the effect of stimulation as a difference from the baseline

performance levels that are derived from our titration of task difficulty. Therefore, the primary analysis will use a mixed-measures ANOVA with one within-participants factor (before and during stimulation) and one between-participants factor (delta-beta, placebo). With an effect size of 0.288 partial-eta square, we estimate that we need at least 21 participants to reach 80% statistical power with a correlation of 0.7. Using a conservative estimate of 0.5 correlation between estimates, we still reach 93% statistical power with 48 participants.

[figure not shown]

Figure 3. Power calculation for the impact of delta-beta tACS on performance tested with ANOVA: between-participants factor of stimulation type and within-participants factors before versus after stimulation. Interaction effect was modeled as a within-between ANOVA using the G*Power software: 3 groups, 2 measurements, partial-eta square 0.288, correlation between estimates conservatively at 0.5. Proposed number of participants, 48, is depicted in red.

Data will be collected until we reach 48 participants. Given the similarity in stimulation methodology between the current experiment and our previous experiment (Riddle, McFerren et al. 2021), we anticipate adequate levels of power for hypothesis testing with 48 total participants.

Secondary outcome: Cross-frequency transcranial alternating current stimulation (tACS) to lateral frontal cortex at delta-beta frequency will increase delta-beta coupling relative to placebo stimulation.

Previous Data: The planning and refinement of the proposed study was informed by our previous experiment that serves as preliminary data for the proposal. In our previous experiment, we delivered cross-frequency tACS to lateral frontal cortex at delta-beta frequency to modulate performance on a cognitive control task relative to placebo stimulation (Riddle, McFerren et al. 2021). As in the current proposal, resting-state EEG sessions were included between each task block such that phase amplitude coupling could be estimated with data that was not corrupted by the stimulation artifact from tACS. In

the previous experiment, we found that delta-beta tACS increased delta-beta coupling with an effect size of 0.382 and a sample size of 23 participants.

Sample Size Determination and Power Calculation: Our previous effect size based on the modulation of delta-beta coupling from delta-beta tACS used a crossover design. The experiment proposed here will use a parallel arm design; however, we will calculate the effect of stimulation as a difference from the baseline coupling levels that are derived from resting-state EEG prior to stimulation. Therefore, the primary analysis will use a mixed-measures ANOVA with one within-participants factor (before and during stimulation) and one between-participants factor (delta-beta or placebo). With an effect size of 0.382, we estimate that we need at least 21 participants to reach 80% statistical power. With 48 participants, then we expect power to exceed 95% with a conservative estimate of 0.5 correlation between estimates.

[figure not shown]

Figure 4. Power calculation for the impact of delta-beta tACS on delta-beta coupling. Interaction effect was modeled as a two-way ANOVA with factors: within-participant before or after stimulation and between-participant factor of stimulation type (delta-beta tACS, theta-gamma tACS, or placebo) using the G*Power software. Number of groups = 3, number of measurements = 2, effect size = 0.382, correlation between estimates conservatively at 0.5. Proposed total number of participants is 48 depicted in red.

Data will be collected until we reach 48 participants. Given the similarity in stimulation methodology between the current experiment and our previous experiment (Riddle, McFerren et al. 2021), we anticipate adequate levels of power for hypothesis testing with 48 total participants.

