9.1 STATISTICAL HYPOTHESES

- Primary Outcome hypothesis:
 - Null: There is no difference in goal-directed behavior between baseline EEFRT and EEFRT during stimulation as a function of stimulation type (delta-beta tACS, theta-gamma tACS, or active-sham).
 - Alternate: There is a difference in goal-directed behavior between baseline EEFRT and EEFRT during stimulation as a function of stimulation type (delta-beta tACS, theta-gamma tACS, or active-sham).
- Secondary Outcome hypothesis:
 - Null: There is no difference in delta-beta phase-amplitude coupling strength between prefrontal electrodes and left motor electrodes for post-stimulation resting-state periods as a function of stimulation type (delta-beta tACS, theta-gamma tACS, or active-sham).

- Alternate: There is a difference in delta-beta phase-amplitude coupling strength between prefrontal electrodes and left motor electrodes for post-stimulation resting-state periods as a function of stimulation type (delta-beta tACS, theta-gamma tACS, or active-sham).
- Exploratory Outcome hypothesis 1:
 - Null: The impact of delta-beta tACS on goal-directed behavior is not correlated with motivation symptom severity.
 - Alternative: The impact of delta-beta tACS on goal-directed behavior is correlated with motivation symptom severity.
- Exploratory Outcome hypothesis 2:
 - Null: Functional connectivity during the resting-state between dorsal striatum and lateral prefrontal cortex is not predictive of the impact of delta-beta tACS on goal-directed behavior.
 - Alternative: Functional connectivity during the resting-state between dorsal striatum and lateral prefrontal cortex is predictive of the impact of delta-beta tACS on goal-directed behavior.

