9.4 STATISTICAL ANALYSES

9.4.1 GENERAL APPROACH

All testing described below assumes a significance threshold of $p = 0.05$. Analyses will be deemed to be statistically significant if the p -value is less than this threshold. An analysis that does not exceed this threshold will be considered inconclusive. Continuous data will be described using means, standard deviations, and confidence intervals, while categorical data will be described using counts/percentages.

There may be additional covariates included in the analysis. Data will be assessed for normality and, if deemed necessary, corrective procedures will be applied (e.g., log normalization). Based on our previous dataset, we expect that the variables used here will be approximately Gaussian. However, if the distribution of a variable displays a skewed tail and a test for normality fails, then it is justified to use a corrective procedure. This correction will be applied upon consideration of the variables themselves, and not based on the result of the intended analysis.

Data will be collected until 48 participants complete the first session and all data is usable. Given that there is only a single session, we expect to have complete data and all analyses will include the full participant pool. However, if there are technical errors that are not caught in time, then the affected analyses may have less participants. In this scenario, the data for a participant is then completely removed from the analysis. We emphasize that lost data is typically of greater concern for longitudinal and multi-session studies. If a subset of participants does not complete the second session in this experiment, then only the analysis of exploratory outcome 2 will be affected.

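### The 93% power for the primary outcome rests on a prior interaction effect of 0.288; the placebo-referenced effect of 0.480 that section 9.2 calls its comparison of interest is never used, and at that effect power is about 26% (range about 15% to 74%).

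*Combined protocol and SAP*

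**What the plan says.** Section 9.2 states the primary outcome for sizing purposes as delta-beta tACS that "will increase goal-directed behavior relative to placebo stimulation". It then reports two results from one earlier 23-person crossover study in a cognitive control task:

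- a "significant interaction between stimulation (delta-beta tACS or theta-gamma tACS, minus placebo) and our cognitive control dimension of interest", for which it reports 0.288, labelled a partial eta-squared, from 23 participants;
- for what it calls the specific comparison of interest, "we found increased reaction time relative to placebo with an effect size of 0.480 from pair-wise t-test", also with N = 23.

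Only the first enters the power calculation. The text describes the model as having "one between-participants factor (delta-beta, placebo") as its levels, while the Figure 3 legend gives 3 groups, 2 measurements and a correlation of 0.5. The results are 21 participants for 80% power at correlation 0.7 and, at correlation 0.5, "we still reach 93% statistical power with 48 participants". Section 9.2 concludes that power will be adequate.

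The primary analysis in section 9.4.2 is the three-arm time-by-stimulation interaction with SHAPS as a covariate, followed by Tukey comparisons.

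**The concern.** The effect that sets the power and the effect that matches the stated aim are different quantities. If the earlier stimulation factor had two levels, each with the same placebo subtracted, placebo drops out of the contrast between them. The 0.288 then measures how far two active waveforms differ across a task dimension. It could be large even if delta-beta did not differ from placebo at all. The figure that does refer to placebo sits in the next sentence, unused.

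At stake is how readers judge the sample size. A trial described as having 93% power will be taken as well able to detect a delta-beta effect over sham of the size seen before. On the plan's own placebo-referenced figure, under its most natural reading, such an effect would be missed about three times in four.

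**Working it through.** **Inputs.** The level comes from section 9.4.1 ("All testing described below assumes a significance threshold of $p = 0.05"). The test is two-sided, because the alternative in section 9.1 is non-directional ("There is a difference in goal-directed behavior between baseline EEFRT and EEFRT during stimulation as a function of stimulation type"). Section 4.1 expects 8 participants in each of 6 cells, so 16 per arm. The effects 0.288 and 0.480 (N = 23) are from section 9.2. Section 9.2 does not name the type of effect size for 0.480.

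**Step 1: reproduce the plan.** For a within-between interaction, λ = f² × N × m / (1 − ρ), with 2 and N − 3 df.

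- 0.288 entered directly as Cohen's f, N = 48, m = 2, ρ = 0.5: λ = 0.0829 × 48 × 2 / 0.5 = 15.9; power 94.2% (plan: 93%).
- Same entry at ρ = 0.7: 80% power is reached at N = 21 (plan: 21).
- 0.288 converted as the partial eta-squared it is labelled as: f = √(0.288/0.712) = 0.636; power about 100% at N = 48, and N = 8 suffices at ρ = 0.7. This does not match the plan.

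So the plan's figures arise from using 0.288 as f. The implied change-score f is √(15.9/48) = 0.576. If theta-gamma equals sham, delta-beta must exceed both by 0.576 × 3/√2 = 1.22 SD of change, which is 1.22/0.48 = 2.5 times 0.480.

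**Step 2: what 0.288 contrasts.** (delta-beta − placebo) − (theta-gamma − placebo) = delta-beta − theta-gamma. This holds if the factor had the two levels that the wording suggests.

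**Step 3: delta-beta v sham at 0.480.** Assume that 0.480 is a paired d and that the SD of change equals the SD of the crossover differences. The noncentrality is 0.480 × √(16/2) = 1.36.

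| Test | Power |
|---|---|
| Two-sample t, 30 df | 26.0% |
| Pooled three-arm error, 45 df | 26.4% |
| Tukey-adjusted, 45 df | 15.4% |

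**Step 4: the planned three-arm interaction**, as an F-test on change with 2 and 45 df. Here λ = 16 × the sum of squared deviations of the arm means.

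| Delta-beta, theta-gamma, sham | λ | Power |
|---|---|---|
| 0.48, 0, 0 | 2.46 | 25% |
| 0.48, 0.24, 0 | 1.84 | 20% |
| 0.48, −0.48, 0 | 7.37 | 65% |

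**Step 5: other readings of 0.480** (delta-beta v sham, before Tukey).

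- Raw-SD units with correlation 0.7: d = 0.480/√(2 × 0.3) = 0.62; power about 40%.
- Rescaled by √2: d = 0.68; power about 46%.
- A partial eta-squared: dz = √(0.48/0.52 × 22/23) = 0.94; power 73-74%.

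**Step 6: how much is the comparator.** Put 0.288 on the same footing, assuming 1 and 22 df: F = 0.288/0.712 × 22 = 8.90, and dz = √(8.90/23) = 0.62. With 16 per arm this gives 40-41%. The comparator is therefore worth about 40 − 26 = 14 points.

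**Step 7: detectable difference.** With 16 v 16, two-sided 0.05 and 80% power, d is about 1.01 (45 df) or 1.02 (30 df), before Tukey.

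**The case against.** Several counter-arguments have force.

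- **The primary test is not delta-beta v sham alone.** The objective in sections 1.1 and 3 names no placebo comparator, and sections 9.1 and 9.4.2 specify a three-arm interaction in which theta-gamma is a legitimate comparator. This stands, and it is why step 4 is needed. It does not rescue the 93%: at 0.480 the three-arm test has 20-25% power, or 65% if theta-gamma acts in the opposite direction.
- **The source study is not visible.** Section 9.2 gives no factor levels or degrees of freedom for 0.288, and the 0.480 sentence does not itself name delta-beta. That placebo cancels, and that 0.480 is delta-beta v placebo, are readings of the wording. Both fit the text, but neither is proven.
- **26% is assumption-bound.** It carries a reaction-time effect from a cognitive control task over to percentage of hard choices in depressed participants, and it ignores any gain from the SHAPS covariate. This also stands, so 26% should not simply replace 93%. If 0.480 were a Cohen's f, power would exceed 93%, but that is not a natural effect size for a paired t-test.

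A reader might infer that the choice of comparator takes power from 93% to 26%. It does not: step 6 puts its share at about 14 points. Nor would correcting the entry of 0.288 on its own lower the figure, since the proper conversion raises it to about 100%. The fall appears when the prior result is expressed as a between-arm difference in change.

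A reader might also infer that a null result is set to be read as evidence against delta-beta tACS. Section 9.4.1 says that a non-significant result will be considered inconclusive.

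**Conclusion.** The concern holds in a limited form. Section 9.2 does not use the effect that it calls its comparison of interest, and the stated 93% is not delivered at that effect on any natural reading of a paired t-test effect size. The central figure is about 26% for delta-beta v sham. It depends on 0.480 being a paired d and on equal SDs for crossover differences and change scores. Across the readings checked, power runs from about 15% to 74%.

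Most of the distance from 93% is not a matter of comparator. It comes from entering 0.288 as Cohen's f in the within-between calculation at correlation 0.5, which presumes a separation of about 1.2 SD of change. The documents do not support putting the whole gap down to the wrong contrast, or treating 26% as an established value. The statement that depends least on assumptions is the detectable difference of about 1.0 SD of change.

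**What to change.** In section 9.2 and the Figure 3 legend, for the primary outcome:

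- Replace the 93% and adequate-power statements with the detectable difference: 48 participants, 16 per arm, detect a delta-beta v sham difference of about 1.0 SD of change with 80% power at two-sided 0.05, before Tukey adjustment.
- Report power at 0.480 as a range, naming the type of effect size and the SD assumption: about 26% under the paired-d reading, and about 20-25% for the three-arm interaction unless theta-gamma acts in the opposite direction.
- Describe N = 48 as pilot-sized, in line with section 4.1.
- Keep 0.288 only as background on the earlier study. The 21-participant figure has the same basis and should go with it.

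This costs a rewording and a less favourable stated power. Enrolment, procedures and the planned analysis stay as they are.

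### Section 9.2, primary power: 21 participants and 93% do not follow from a partial eta-squared of 0.288, and the two-level factor in the text conflicts with the three-arm analysis

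*Combined protocol and SAP*

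**What the plan says.** All of this is in Section 9.2 of the combined protocol and SAP unless stated.

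- **Source of the effect.** The earlier 23-person study reported this result: "significant interaction between stimulation (delta-beta tACS or theta-gamma tACS, minus placebo) and our cognitive control dimension of interest with a partial-eta square of 0.288". The protocol discloses the design: "Our previous effect size based on behavioral modulation from delta-beta tACS used a crossover design".
- **First figure.** "With an effect size of 0.288 partial-eta square, we estimate that we need at least 21 participants to reach 80% statistical power"; the correlation for this figure is set at 0.7.
- **Second figure.** "Using a conservative estimate of 0.5 correlation between estimates, we still reach 93% statistical power with 48 participants".
- **Model in the Figure 3 legend.** A within-between interaction in G*Power, specified as: "3 groups, 2 measurements, partial-eta square 0.288, correlation between estimates conservatively at 0.5".
- **Model in the text.** The primary-outcome paragraph describes "one between-participants factor (delta-beta, placebo"), and the secondary-outcome paragraph "one between-participants factor (delta-beta or placebo").
- **Conclusion drawn.** "we anticipate adequate levels of power for hypothesis testing with 48 total participants".

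The hypotheses in 9.1 and the analyses in 9.4.2 and 9.4.3 use a stimulation factor with three levels: delta-beta, theta-gamma and active sham. Section 4.1 expects 8 participants in each of 6 arm-by-stratum cells, so 16 per arm. Section 9.2 does not convert 0.288 to Cohen's f and does not name the G*Power effect-size option.

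**The concern.** A partial eta-squared of 0.288 is a very large effect once converted to Cohen's f and combined with a repeated-measures correlation. A requirement of 21 participants and a power of only 93% at 48 looked too modest for it. The text also counts two groups where the legend beneath it counts three, and the group count changes the answer.

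Section 9.2 is the only quantitative justification for 48 participants, and this calculation covers the primary outcome. If its figures do not follow from their stated input, a reader cannot tell what size of effect the trial was planned to detect, and anyone planning a later study from this one would inherit the ambiguity.

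**Working it through.** **Inputs.** Effect 0.288; correlation (rho) 0.7 for the 21 and 0.5 for the 93%; m = 2 measurements; k = 3 groups (Figure 3 legend, 9.1, 9.4.2); N = 48; alpha 0.05 (9.4.1).

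**Test.** Interaction F test with df1 = (k−1)(m−1) = 2 and df2 = (N−k)(m−1), which is 45 at N = 48. Power comes from the noncentral F distribution with noncentrality λ.

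**1. The label taken at face value.** f² = 0.288/(1−0.288) = 0.288/0.712 = 0.4045, so f = 0.636. The protocol does not say how f enters the noncentrality, so three conventions were tried, all with k = 3:

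| Convention | λ | Minimum N for 80% | Power at N = 48 |
|---|---|---|---|
| Default, uses rho | f²·N·m/(1−rho) | 8 at rho 0.7 (9 with equal arms) | over 99.9% at rho 0.5 |
| SPSS-type, no rho | f²·(N−k) | 30 | 96.7% |
| Cohen-type, no rho | f²·N | 28 (30 with equal arms) | 97.5% |

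At N = 48, λ is 0.4045×48×2/0.5 = 77.7, 0.4045×45 = 18.2 and 0.4045×48 = 19.4 respectively. No row gives 21 and 93%. The last two do not use a correlation at all, yet 9.2 attaches one to each of its figures. Under those two conventions, N = 21 gives 59.5% and 66.7% power.

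**2. Reproducing the plan's figures.** Enter 0.288 directly as Cohen's f in the default formula, so f² = 0.288² = 0.0829, with k = 3:

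- N = 21, rho 0.7: λ = 0.0829×21×2/0.3 = 11.61, power 80.6%. The minimum N is 21, an exact match.
- N = 48, rho 0.5: λ = 0.0829×48×2/0.5 = 15.93, power 94.2%, about one point above the stated 93%. Exactly 93% would need f = 0.280.

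**3. Which group count fits.** With f = 0.288 and k = 2, the minimum N at rho 0.7 is 17 (18 with equal arms) and power at N = 48, rho 0.5 is 97.4%. The stated figures therefore fit three groups, not the two in the text.

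**4. What f = 0.288 means as a partial eta-squared.** Ignoring the correlation, 0.0829/1.0829 = 0.077. The default formula then divides by 1−rho. At rho 0.5 and N = 48, the partial eta-squared on the change scores is 15.93/(15.93+48) = 0.249, or 15.93/(15.93+45) = 0.261 using df2. So it is about 0.25.

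**5. Secondary outcome.** The 0.382 has no stated metric. As Cohen's f with k = 3 and rho 0.5, it gives a minimum N of 20 (21 with equal arms) and 99.8% at N = 48, in line with the stated 21 and more than 95%. As a partial eta-squared under the Cohen-type convention it gives 19 (21 with equal arms) and 99.8%. The figures hold either way, so they do not settle which metric was used.

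**The case against.** The strongest reply is that nothing turns on this. Taken as an observed partial eta-squared without applying the correlation again, 0.288 gives 96.7% to 97.5% at N = 48, so the stated 93% is slightly cautious. The contrast with 8 participants and over 99.9% is the least informative one, because the default formula inflates an effect that already came from a within-person design. Three arms is clear from the rest of the document, so the two-level wording is a slip. The crossover source is disclosed, and Section 4.1 calls the study a pilot.

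Most of that stands, and it limits the point. It does not make 21 and 93% follow from their stated input. The nearest rescue is a partial eta-squared of 0.288 with two groups under the Cohen-type convention: 22 participants, and 93.6% with two arms of 16 (N = 32). That contradicts the stated 48 and the three groups, and it leaves the quoted correlations with no role.

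A reader might draw four stronger conclusions that the documents do not support:

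- **The trial is underpowered.** At N = 48 neither reading of 0.288 shows this.
- **The sponsor certainly entered 0.288 as f.** One figure matches exactly and the other only closely, and the plotted curve is not available to check.
- **The calculation assumed about a quarter of the cited effect (0.077 against 0.288).** At rho 0.5 the like-for-like value on change scores is about 0.25.
- **The error is always on the safe side.** That holds at N = 48. Under the conventions without a correlation, 21 participants would be too few.

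**Conclusion.** The power statement is wrong as written in two respects. First, 21 participants and 93% do not follow from a partial eta-squared of 0.288 under any of the three conventions tried; they are consistent with 0.288 having been entered as Cohen's f (21 exactly, 94.2% against 93%). Second, both power paragraphs name two levels for a factor that has three in the figure legends and in 9.1, 9.4.2 and 9.4.3.

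The consequence is limited. With three groups and the protocol's rho of 0.5, power at N = 48 is 94.2% if 0.288 is Cohen's f and at least 96.7% if it is a partial eta-squared. The first of these depends on rho: at f = 0.288 it falls to 84.0% at rho 0.3 and 78.5% at rho 0.2. All these figures are before the SHAPS covariate and take 0.288 as given. Whether an effect from a crossover study on a different task carries over to this parallel design is a separate and disclosed uncertainty. No error is claimed in the secondary-outcome figures.

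**What to change.** Change the wording of Section 9.2 only.

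1. In both power paragraphs, write the between-participants factor with three levels (delta-beta, theta-gamma, active sham), to agree with the figure legends and the planned analyses.
2. Confirm what was entered in G*Power, then do one of the following:
   - state 0.288 as an assumed Cohen's f, with its correlation and a reason for assuming it (minimum N 21 at rho 0.7; about 94% at N = 48, rho 0.5); or
   - recompute from the partial eta-squared and name the effect-size option (for example 30 and 96.7%, or 28 and 97.5%).

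   Either way, stop presenting 21 and 93% as following from a partial eta-squared of 0.288, and correct the Figure 3 legend to match.
3. Name the metric of 0.382 for the secondary outcome.

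A sentence on the difference between arms that 16 per arm can detect would help readers, but it is optional and not part of the error.

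The cost is one check of the saved power calculation and a few lines of text. The sample size, arms, analysis and conduct do not change.
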